The proposed study is a phase 2, open-label study of tofakinib in treatment of patients with chronic pouchitis. Patients with chronic active pouchitis will be recruited from the Cedars-Sinai Inflammatory Bowel Disease Center. The total expected duration of participation is 16 weeks including a 4-week screening period, 8 weeks of tofakinib therapy and an end of study visit 4 weeks after completion of 8-week tofakinib treatment. Subjects experiencing early withdrawal from study will be scheduled for a safety follow-up visit 4 weeks after the date of withdrawal. The primary outcome is a reduction in the mPDAI score ≥ 2 at week 8 compared to baseline. We will also assess secondary outcomes including changes in clinical symptoms, fecal calprotectin, HRQOL, and mucosal appearance.

Figure 1: Study Design

Study Population

The study will be open to adult patients (ages 18-80 years) seen at the Cedars-Sinai Inflammatory Bowel Disease Center who meet eligibility criteria.

Inclusion criteria

1. Male or female subjects ages 18 to 80

2. Subjects with a history of proctocolectomy with ileal pouch anal anastomosis (IPAA) for UC at least 6 months prior to screening.
3. Subjects with pouchitis that is chronic, defined by a mPDAI score ≥ 5 assessed as the average from 3 days immediately prior to the baseline study visit and a minimum endoscopic subscore of 2 (outside the staple or suture line) with either (a) ≥ 3 recurrent episodes within 1 year prior to the screening treated with ≥ 2 weeks of antibiotic or other prescription therapy, (b) requiring maintenance antibiotic therapy taken continuously for ≥ 4 weeks immediately prior to the baseline study visit, or (c) not responding to $>= 4$ weeks of antibiotic therapy.
4. Women of childbearing potential must have documentation of a negative pregnancy test at screening and must agree to use two highly effective methods of birth control during the study and for at least 1 month after completion of study drug dosing.
5. Subjects willing and able to give informed consent.

Exclusion criteria

1. Subjects with IPAA surgery done for Crohn's disease (CD) or familial adenomatous polyposis (FAP) indications.
2. Subjects with CD-like complications including non-anastomotic strictures and active perianal fistulae, isolated or predominant cuffitis or mechanical complications of the ileal pouch.
3. Surgical complications such as anal stenosis, anastomotic leak, or fistula.
4. Subjects with prior exposure to tofacitinib.

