The primary outcome of the study is clinical response at 8 weeks (defined below) as a measure of treatment efficacy. Other efficacy endpoints will include individual clinical, biochemical, and endoscopic assessments. Key secondary outcomes include assessment for safety and health-related quality of life.

Primary Endpoint

1. Proportion of subjects with clinical response defined as reduction in mPDAI score ≥ 2 from baseline at 8 weeks.

Secondary Endpoints

1. The proportion of subjects with clinical response, defined as an mPDAI score of ≥ 5 at 8 weeks with ≥ 2 -point decrease from the baseline score at 8 weeks.
2. The proportion of subjects with clinical remission at 8 weeks, defined as mPDAI score of < 5 with a ≥ 2 -point decrease from the baseline mPDAI score.
3. Change in mPDAI score at 8 weeks compared to baseline.
4. Change in mPDAI clinical sub-score at week 4 and week 8 compared to baseline.
5. Change in mPDAI endoscopic sub-score at week 8 compared to baseline.
6. Change in IBD-related quality of life as measured by Cleveland Global Quality of Life (CGQL) at week 4 and week 8 compared to baseline.
7. Safety, as determined by incidence of treatment-emergent adverse events. Adverse events of interest will include thromboembolic events and herpes zoster.

Efficacy Assessments

Efficacy measurement

The following will be used for definitions of clinical, biochemical, and endoscopic efficacy:

1. Clinical response defined as an mPDAI score of ≥ 5 at 8 weeks with a 2-point decrease from the baseline mPDAI score.
2. Clinical remission defined as mPDAI score < 5 after 8 weeks of treatment.
3. Change in mPDAI score from baseline to week 8.
4. Change in clinical and endoscopic mPDAI sub-scores from baseline to week 8.
5. Change in fecal calprotectin from baseline to week 8.
6. Change in serum C-reactive protein from baseline to week 8.

Symptom Diary

The subjects will be required to maintain a paper-based symptom diary to be completed daily starting after the initial screening visit. The symptoms recorded will include frequency of bowel movements, fecal urgency, abdominal pain/cramps, fever and blood in stools. The symptoms during the 3 days preceding the study visits will be used for the calculation of the mPDAI score for each study visits.

Pouch disease activity

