Study subject demographics (age, gender, race), baseline characteristics (height, weight, and BMI), IBD history, prior IBD-related medication use, concomitant medications and baseline laboratory tests will be reported using descriptive statistics. All subjects in the study who received at least one dose of the study drug will be included for analysis. Missing data or early termination will be handled by non-responder imputation. Remission and response rate will be assessed using descriptive statistics. Change in mPDAI, CGQL scores, serum CRP and fecal calprotectin compared to baseline will be assessed using Wilcoxon signed-rank test. Adverse events will also be reported using descriptive statistics. Data will be considered significant at the two-sided p value of <0.05 where applicable.

Publication Plan

After the completion of the study and analysis of the data, we will submit the results of this study to national gastroenterology meetings (ie. Digestive Disease Week or American College of Gastroenterology Annual Meeting) followed by manuscript submission for publication in a high impact peer-reviewed journal.

Anticipated Project Timeline

Based on the clinical volume at Cedars-Sinai Medical Center, we anticipate enrolling 12 subjects in this research study over a period of 28 months. Last patient study visit will be 12 weeks later. This will be followed by data analysis and writeup/submission of study abstract and manuscript.

Task	Month											
	1-2	3-4	5-6	7-10	11-14	15-18	19-22	23-26	27-30	31-34	35-36	37-39
Obtain IRB approval												
Enrollment												
Final study visit												
Data analysis												
Prepare / submit abstract												
Prepare / submit manuscript												

References

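### Clinical response and remission each carry two conflicting definitions, and the response definition in the Efficacy measurement list excludes every remitter

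*Combined protocol and SAP*

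**What the plan says.** The primary endpoint is stated twice, consistently. Overview of Study Design has "The primary outcome is a reduction in the mPDAI score ≥ 2 at week 8 compared to baseline", and Primary Endpoint has "Proportion of subjects with clinical response defined as reduction in mPDAI score ≥ 2 from baseline at 8 weeks". Neither limits the week-8 score.

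The opening of Evaluation and Outcomes names clinical response as the primary outcome and points forward for its definition. Three further statements then bear on the same terms:

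- Secondary Endpoints, item 1, reuses the label: "The proportion of subjects with clinical response, defined as an mPDAI score of ≥ 5 at 8 weeks", together with a fall of at least 2 points.
- Secondary Endpoints, item 2: "The proportion of subjects with clinical remission at 8 weeks, defined as mPDAI score of < 5 with a" fall of at least 2 points from baseline.
- Efficacy measurement opens with "The following will be used for definitions of clinical, biochemical, and endoscopic efficacy". Its item 1 is "Clinical response defined as an mPDAI score of ≥ 5 at 8 weeks with a 2-point decrease from the baseline mPDAI score" and its item 2 is "Clinical remission defined as mPDAI score < 5 after 8 weeks of treatment".

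Data Analysis says only "Remission and response rate will be assessed using descriptive statistics". It points to none of these definitions.

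**The concern.** One label, clinical response, is attached to two different sets of subjects. The version with a floor of 5 on the week-8 score sits in the list that claims to supply the definitions, so an analyst could reasonably program it as the response rate. That rate would leave out the subjects who did best: a fall from 12 to 0 would count as no response.

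Remission has a smaller version of the same problem. Without the required 2-point fall, a subject can be in remission and still fail the primary endpoint, so remission is no longer contained in response.

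This is a single-arm, open-label pilot with no sample size calculation, so the response rate is the main result. Two live definitions also leave room to choose between them after the data are seen.

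**Working it through.** The plan gives no sample size, power or error-rate figure for these endpoints, so there is none to reproduce. The check is to classify every possible pair of scores under each definition.

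**Inputs**
- Baseline mPDAI at least 5 (Inclusion criteria, item 3).
- Score range 0 to 12, taken from the two 6-point sub-scores under Pouch disease activity (an inference).
- 12 subjects anticipated (Anticipated Project Timeline).
- Item 1's 2-point decrease read as at least 2, unless stated otherwise.

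Write b for baseline and w for week 8.

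| Definition | Rule |
|---|---|
| Primary endpoint | b − w ≥ 2 |
| Secondary endpoint 1; Efficacy measurement item 1 | w ≥ 5 and b − w ≥ 2 |
| Secondary endpoint 2 (strict remission) | w < 5 and b − w ≥ 2 |
| Efficacy measurement item 2 | w < 5 |

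**Whole-point scores.** There are 8 baselines (5 to 12) and 13 week-8 values (0 to 12), so 8 × 13 = 104 pairs. These are counts of score pairs, not expected shares of patients.

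- Primary: b − 1 values of w qualify at each baseline, so 4 + 5 + … + 11 = 60.
- With the floor: w runs from 5 to b − 2, giving b − 6 values for b ≥ 7, so 1 + 2 + … + 6 = 21. No baseline below 7 qualifies, because w ≥ 5 and b − w ≥ 2 together require b ≥ 7. If item 1 meant a fall of exactly 2, only 6 pairs would qualify.
- Strict remission: 4 values at b = 5 and 5 at each of the other seven baselines, so 4 + 35 = 39.
- Below 5 alone: 8 × 5 = 40. The one extra pair is 5 to 4, a fall of 1.

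So 60 = 21 + 39 with no overlap: secondary endpoints 1 and 2 split the primary endpoint exactly. Efficacy measurement items 1 and 2 together give 21 + 40 = 61, one pair too many.

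**Scores in thirds.** Inclusion criteria item 3 uses a 3-day average, so thirds are possible (an assumption). There are then 22 × 37 = 814 pairs. The primary endpoint covers 451 = 136 + 315, the same exact split. Below 5 alone covers 330, so the two remission definitions differ in 330 − 315 = 15 pairs, at baselines from 5 to 6.33. The floor still excludes every baseline below 7.

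**Effect on the reported rate.** Because the split is exact,

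response rate with the floor = primary rate − strict remission rate.

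With 12 subjects the gap is (number of strict remitters)/12, and 1/12 = 8.3 points for each. Two illustrations with assumed counts and exact 95% intervals:

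| Remitters | Other responders | Primary endpoint | With the floor |
|---|---|---|---|
| 4 | 4 | 8/12 = 67% (35 to 90%) | 4/12 = 33% (10 to 65%) |
| 6 | 0 | 6/12 = 50% (21 to 79%) | 0/12 = 0% (0 to 26%) |

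For scale only, the background section cites remission rates of 10% and 37% for anti-TNF agents. Applied to 12 subjects they give 12 × 0.10 = 1.2 and 12 × 0.37 = 4.44, or about 1 to 4 remitters and a gap of about 8 to 33 points.

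**The case against.** The strongest reply is that the primary endpoint is clear and the rest is loose labelling. The first items of the Efficacy measurement list follow the secondary endpoints in content and order, so item 1 may simply restate secondary endpoint 1. Response without remission and remission would then be two exclusive categories that add up to the primary endpoint, and leaving out remitters would be the purpose of the first. Moreover, the rates are descriptive, the Wilcoxon tests use score changes that do not depend on these definitions, and every version can be computed from the baseline and week-8 scores, so no data are lost.

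Much of this stands. The primary endpoint can be identified, secondary endpoint 1 is probably meant as response without remission, and no test is affected. The remission mismatch is narrow. The anti-TNF rates concern another drug class in antibiotic-refractory disease, one of them over the long term, so they say nothing about this trial's likely result.

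The benign reading, however, has to be inferred. Nowhere does the plan call item 1 or secondary endpoint 1 response without remission. Both use the primary endpoint's own label, and item 1 sits in the list offered as the definitions. That data can be re-analysed later does not settle in advance which rate is the result.

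**Conclusion.** The concern holds. Efficacy measurement item 1 is wrong as written: it contradicts the primary endpoint on the term that defines it and removes every strict remitter from response. The gap is the strict remission rate, 8.3 points per remitter with 12 subjects. This identity needs no assumption about the data, only that item 1's decrease is read as at least 2; the actual size depends on the number of remitters, which is unknown.

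Item 2 also conflicts with secondary endpoint 2, but to a minor extent: one pair in 104 in whole points, or 15 in 814 if scores fall in thirds. The consequence is wrong or unreadable response and remission rates. It does not affect any error rate or power.

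**What to change.** - **Efficacy measurement, item 1:** define clinical response as in the primary endpoint, a reduction in mPDAI of at least 2 from baseline at week 8, whatever the week-8 score.
- **Secondary endpoint 1:** relabel it as response without remission.
- **Efficacy measurement, item 2:** add the fall of at least 2 points, to match secondary endpoint 2 and make remission a subset of response.
- **Data Analysis:** state that the response and remission rates use these definitions.

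Relabelling item 1 as response without remission, with its decrease written as at least 2, would also remove the contradiction, provided the primary definition is then named as the one for clinical response. Either way the cost is a wording change in the protocol, with no extra data, visits or patients.

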18. Subjects with condition(s) that in the opinion of the study investigators, may interfere with the participants ability to comply with the study procedures.

Concomitant medications

Study subjects will be allowed to remain on permitted concomitant medications provided the patient is on a stable dose for \geq 2 weeks prior to starting tofacitinib. Patient will need to stay on stable doses of these medications for the study duration of 8 weeks.

1. Antibiotics
2. Antidiarrheal agents
3. Oral corticosteroids including budesonide, up to doses of prednisone 20mg daily (or equivalent), or budesonide 9mg daily.
4. Probiotics

The following medications will not be allowed during the study:

1. Azathioprine, 6-mercaptopurine, or methotrexate within the 28 days prior to dosing visit.
2. Adalimumab, infliximab, golimumab, etanercept, certolizumab or vedolizumab within the 60 days prior to the first study visit or with negative drug concentration
3. Ustekinumab within 120 days prior to the first dosing visit or with negative drug concentration.
4. Intravenous corticosteroids within the 14 days prior to the first dosing visit.
5. Topical mesalamine or topical steroid within the 14 days prior to the first dosing visit.
6. Mycophenolic acid, tacrolimus, or cyclosporine within 60 days prior to the first dosing visit.

Treatment with Tofacitinib

Eligible subjects will be given tofacitinib 10mg twice daily for an 8-week duration. Study drug will be supplied for 4 weeks each at the baseline and week 4 visits.

Study Visits and Procedures

There are 5 study visits and 2 pouch endoscopic procedures during this 12-week study.

Screening Period (Week -4 to Day 0)

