After giving informed consent, subjects will undergo up to a 4-week screening period to provide baseline data and be assessed for eligibility. The subjects will have a screening visit during which they will undergo an assessment of their medical history, symptom assessment and a complete physical examination with vital signs, height and weight measurement. They will also undergo complete blood count with automated differential, serum chemistries, serum C-reactive protein (CRP), lipid panel, QuantiFERON®-TB Gold test, urinalysis, fecal calprotectin, infectious stool studies, electrocardiogram (ECG), and chest X-ray. Subjects who satisfy the inclusion criteria and do not meet any exclusion criteria will proceed with pouch endoscopy with biopsies to confirm endoscopic eligibility and assess a baseline mPDAI endoscopic subscore. The pouch endoscopy will be scored by a central reader to reduce the risk of bias. If the subject meets all the eligibility criteria, he/she may be enrolled into the study. The subjects will be required to maintain a daily paper-based symptom diary starting immediately after the screening visit, although only symptoms during the 3 days preceding the study visits will be used for the calculation of the mPDAI score for the appropriate study visits.

Baseline Visit (Week 0)

At the baseline visit, subjects' eligibility for the study will be confirmed. Vital signs will be recorded, and a targeted physical examination will be performed. The symptom diary will be reviewed for calculation of the mPDAI score, and subjects will complete the CGQL questionnaire. At the end of the visit, the subjects will be given a 4-week supply of tofacitinib to be taken at a dose of 10 mg twice daily.

Week 4 and Week 8 Visit (± 3 days)

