At the week 4 and week 8 visit, the subjects will undergo assessment for concomitant medication use, adverse effects and compliance with the study drug. Physical assessment will include vital signs and a symptom driven targeted physical examination. Blood, urine and stool will be collected for hematology, chemistry, CRP, urinalysis and fecal calprotectin measurement. Symptom diary will be reviewed, and subjects will complete the CGQL questionnaire. At the end of week 4 visit, the second 4-week supply of the study drug will be dispensed to the subjects. At the end of 8 weeks, the subjects will stop taking the study drug and undergo a pouch endoscopy with biopsies for calculation of mPDAI score to assess treatment response. The pouch endoscopy will be scored by a central reader to reduce the risk of bias.

Week 12 (± 3 days) or Early Termination Visit

The week 12 visit will be the final visit. Subjects who are withdrawn earlier from the study (per study rules and subjects who withdraw consent) after receiving study medication will complete

an early termination visit. At this visit, subjects will undergo a physical assessment, review of medications, adverse event assessment and blood, urine and stool collection for hematology, chemistry, CRP, urinalysis and fecal calprotectin measurement. Symptom assessment and CGQL questionnaire completion will also be performed.

Table 1 - Schedule of Study Procedures and Visits

Study visit	Screening (Week -4 to day 0)	Baseline (Day 1)	Week 4	Week 8	Week 12
General					
Informed consent	x				
Medication/Medical History	x				
Smoking Status	x				
Height, weight, BMI	x	x	x	x	x
Vital Signs	x	x	x	x	x
12-lead ECG	x				
Physical Examination	x	x	x	x	x
Chest X-ray	x				
Tuberculosis and HBV testing	x				
Study Drug Dispensing		x	x		
Clinical, laboratory, endoscopic and safety assessments					
Pregnancy Test (females only)	x				
Urine pregnancy test		x	x		
Chemistry, Hematology, Urinalysis	x		x	x	x
Stool C. difficile test	x				
Fasting Lipid Panel	x		x	x	x
C-Reactive Protein	x		x	x	x
Pouch endoscopy and biopsies	x			x	
Fecal calprotectin	x		x	x	x
Symptom Assessments	x	x	x	x	x
Concomitant medications	x	x	x	x	x
mPDAI		x		x	
Adverse event assessment			x	x	x
CGQL		x	x	x	x

Evaluation and Outcomes

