Pouch disease activity assessment will be done using mPDAI, which is a combination of 6-point clinical and 6-point endoscopic scores. It has been shown to have excellent accuracy for pouchitis disease activity assessment with an area under the receiver operative characteristic curve of 0.995 and a sensitivity and specificity of 97% and 100%, respectively, compared to the pouch disease activity (PDAI) score, which is more complex as it includes histological activity

score in addition to clinical and endoscopic scores¹⁷. mPDAI score will be calculated at each study visit.

[Health-related quality of life](#)

Health related quality of life will be measured using the validated CGQL. The CGQL is a 3-question patient-reported assessment, which asks to rate the following questions on a 0-10 scale, with 0 being worst and 10 being best:

1. Current Quality of Life?
2. Current Quality of Health?
3. Current Energy Level?

Patients will be asked to complete the CGQL questionnaire at each study visit.

[Laboratory markers](#)

Serum CRP and fecal calprotectin will be used as laboratory markers of pouchitis activity. These will be assessed during the screening period and at week 4, 8 and 12 visits.

[Safety Assessment](#)

Subject safety will be assessed on all study visits using standard measures, including vital signs, symptom history, concomitant medication usage history, physical examinations, and blood and urine laboratory tests. Specifically, subjects will be assessed for the known potential adverse events to tofacitinib including anemia, peripheral cytopenias, lipid panel derangements, elevation of liver aminotransferases, thromboembolic events and infections.

[Statistical Methods](#)

[Sample Size Estimation](#)

Since this is a pilot study, no sample statistical sample size estimation was performed.

[Data Analysis](#)

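### CRP and fecal calprotectin have no Day 1 sample, so their change from baseline can include up to four untreated weeks

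*Combined protocol and SAP*

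**What the plan says.** Laboratory markers names serum CRP and fecal calprotectin as the laboratory measures of pouchitis activity and gives their timing: "These will be assessed during the screening period and at week 4, 8 and 12 visits". Table 1 matches this: both rows are marked at screening and at weeks 4, 8 and 12, and the Baseline (Day 1) cells are blank. The Baseline Visit section lists no blood or stool collection. It says "Vital signs will be recorded, and a targeted physical examination will be performed", then adds diary review, the CGQL and dispensing of drug.

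The Screening Period section explains where the pre-treatment value comes from: "subjects will undergo up to a 4-week screening period to provide baseline data and be assessed for eligibility".

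Efficacy measurement lists "Change in fecal calprotectin from baseline to week 8" and the same change for CRP. Data Analysis then states: "Change in mPDAI, CGQL scores, serum CRP and fecal calprotectin compared to baseline will be assessed using Wilcoxon signed-rank test". No section defines any other laboratory baseline or asks for a repeat sample before dosing.

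Under Concomitant medications, some limits count back from dosing and not from the screening sample. One of the exclusions reads: "Topical mesalamine or topical steroid within the 14 days prior to the first dosing visit". Intravenous corticosteroids have the same 14-day limit. Permitted drugs (antibiotics, antidiarrheals, oral corticosteroids, probiotics) must be at a stable dose for at least 2 weeks before tofacitinib starts.

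**The concern.** The Objective 1 hypothesis says that tofacitinib lowers fecal calprotectin. In a single-treatment, open-label study, the two laboratory markers are the efficacy measures that depend on neither patient report nor an endoscopic score. Their change score will naturally be read as change on drug.

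As scheduled, it is change since screening. Anything that moves the marker between that sample and the first tablet enters the paired difference, and the signed-rank test cannot separate it from change after dosing. Three sources are open under the protocol:

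- natural fluctuation or regression to the mean, in a population where one entry route is at least 3 recurrent episodes in a year;
- stopping topical mesalamine, topical steroid or intravenous corticosteroid after the screening sample but at least 14 days before dosing;
- starting or changing a permitted drug between weeks -4 and -2.

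The CGQL and the mPDAI symptom component take their baselines at the Week 0 visit, so the marker results will be reported beside outcomes measured from a different time point.

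**Working it through.** The plan has no sample-size or power figure for these markers (Sample Size Estimation says none was done), so there is no figure to reproduce. The check has three parts.

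**1. Timing.** Inputs: screening up to 4 weeks, treatment 8 weeks, follow-up 4 weeks (Overview of Study Design); visit window ±3 days (Week 4 and Week 8 Visit).

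- Total participation: 4 + 8 + 4 = 16 weeks, as the Overview states.
- Week 8 change: at most 4 untreated weeks out of 4 + 8 = 12, so 4/12 = 33%.
- Week 4 change, if it is tested: at most 4 out of 4 + 4 = 8, so 4/8 = 50%.
- Longest interval from screening sample to week 8 sample: 28 + 56 + 3 = 87 days.

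These are shares of time, not of effect.

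**2. Which drug changes can fall in the gap.**

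- Topical agents and intravenous corticosteroids: the limit is 14 days before dosing, so they can be stopped between days -28 and -14.
- Permitted drugs: stability is required for 2 weeks, so changes can fall in weeks -4 to -2.
- Thiopurines and methotrexate: the limit is 28 days before dosing and screening is at most 28 days, so stopping falls at or before screening.
- Biologics: the 60-day and 120-day limits would normally be complete by screening.

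Only the first two groups can change inside the gap.

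**3. What a pre-dose shift would do.** All shift sizes here are assumptions.

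One-subject illustration: calprotectin 800 at screening, 500 on Day 1, 400 at week 8.

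- Reported change: 1 − 400/800 = 50% fall. On-drug change: 1 − 400/500 = 20% fall.
- With a pre-dose drift of −40%, Day 1 is 480 and the on-drug fall is 1 − 400/480 = 17%.
- With +40%, Day 1 is 1120 and the on-drug fall is 1 − 400/1120 = 64%.

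The same reported 50% fall is thus compatible with an on-drug fall of 17% to 64%.

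Test behavior with 12 complete pairs (the anticipated enrollment) at two-sided 0.05: the exact signed-rank test rejects when the smaller rank sum is 13 or less, with exact size 0.042. A simulation of 200,000 trials with normal paired changes, the shift expressed in SDs of the paired change and no drug effect, gives:

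| Systematic pre-dose fall | Chance of a significant decrease |
|---|---|
| 0 | 2.1% |
| 0.10 SD | 4.3% |
| 0.25 SD | 10.5% |
| 0.50 SD | 31.5% |

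In the other direction, with an assumed true drug effect of 0.8 SD, power is 66.8% with no shift, 37.0% after a pre-dose rise of 0.25 SD and 13.6% after a rise of 0.50 SD.

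With a Day 1 sample the untreated share becomes 0 of 8 weeks (0 of 4 for week 4), and a shift confined to the pre-dose window drops out of the change score.

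**The case against.** The schedule is deliberate and internally consistent: screening is meant to supply baseline data, and the text and Table 1 agree. That is true, so this is not a contradiction or a missing baseline. It does not remove pre-dose movement from the change score.

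Four weeks is a ceiling. That also stands: the screening column runs to day 0, so a sample could be taken close to dosing. However, the Screening Period text places both markers among the screening-visit tests, ahead of the endoscopy and its central reading, so some gap is to be expected.

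The plan has partial safeguards. Inclusion criterion 3 requires an mPDAI of at least 5 based on symptoms in the 3 days before the baseline visit, which removes some subjects whose flare is settling. A high screening endoscopic subscore can still carry the total. Subjects who enter on continuous maintenance antibiotics must have taken them for at least 4 weeks up to baseline, which covers the gap for those antibiotics in that group only.

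Random drift in both directions adds variance without shifting the test. This is correct: only systematic drift biases it. Neither marker is itself an entry criterion, so regression to the mean would act only through correlation with the mPDAI.

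A reader might infer that drift and washout are counted as tofacitinib benefit. The documents support only that they can enter the estimate. Direction is not fixed: stopping an active topical or intravenous steroid would tend to raise the markers and hide an effect.

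A reader might also take the Safety Assessment statement about laboratory tests at all visits as supplying a Day 1 value. It names neither marker, and Table 1 marks no laboratory panel at baseline.

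**Conclusion.** The point holds in a limited form. The only pre-treatment CRP and calprotectin values come from screening, so the tested change can include up to 4 untreated weeks, during which the protocol allows some treatments to change. The result can be an exaggerated effect, a masked effect or extra noise. The documents give no size or direction for the drift, so the percentages above show sensitivity under assumed shifts, 12 complete pairs and normal changes; they are not estimates of bias.

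The consequence is modest. Both markers are listed efficacy measures and calprotectin is in the Objective 1 hypothesis, but neither is the primary or a numbered secondary endpoint. It would go too far to infer that the marker schedule undermines the primary mPDAI response, which uses neither marker, or that a Day 1 sample would allow a fall to be attributed to tofacitinib. Without a control arm, drift during the 8 treated weeks remains.

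**What to change.** Move fecal calprotectin and CRP from the screening column to the Baseline (Day 1) column of Table 1, collected before the first dose. In Data Analysis, define that value as the baseline for the signed-rank tests. Align the Screening Period, Baseline Visit and Laboratory markers text. If a screening value is also kept, do not use it as the analysis baseline.

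The cost is protocol wording plus one blood draw and one stool sample per subject, for about 12 subjects, at a visit that now collects neither. Neither marker is an eligibility criterion, so eligibility does not depend on the screening sample. The number of assays is unchanged if the samples are moved and rises by one set per subject if both are kept. The trade-off is that the marker baseline may then lie further in time from the screening endoscopy, which must stay in screening because it determines eligibility.

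A lighter but weaker alternative is to define baseline as the last pre-dose value and report each subject's sample-to-dose interval. That makes the gap visible but does not close it.
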